#### **Health Economics and Type 1 Diabetes**

Health-economic evaluation models in diabetes, typically microsimulations or Markov models (37), rely on risk equations that capture short- and long-term outcomes influenced by interventions such as improved diagnostics and treatment (38–40). These models link health outcomes to costs and patient benefits, aiding healthcare decision-making and guideline optimisation. Traditionally, models for T1D have been based on the American Diabetes Control and Complications Trial (DCCT) (41), and its follow-up, the Epidemiology of Diabetes Interventions and Complications (EDIC) study (42), alongside frameworks borrowed from Type 2 Diabetes, despite fundamental differences in aetiology, onset and risk factors.

There is a growing need to refine models for T1D evaluation (39,40), including the integration of risk equations derived from more recent patient cohorts, such as Swedish observational data (40). Existing health-economic models predominantly focus on adult populations and long-term vascular complications, with limited data available on children and adolescents. Additionally, mental health effects (43) and other non-vascular complications remain underrepresented. While international research on T1D complications is expanding, it tends to be clinically focused and lacks straightforward applicability to health-economic models.

Understanding the short- and long-term consequences of T1D across the lifespan is increasingly important due to advances in early risk identification, interventions to reduce incidence (44) (GPPAD-POInT at ClinicalTrials.gov IDNCT03364868), and discussions on newborn screening. In this context, health-economic models will support decision-makers in assessing the value of delaying T1D onset in terms of patient outcomes and cost savings.

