### **Health Economics and Type 1 Diabetes**

Research from our group and its collaborators has demonstrated positive trends in T1D complications, including a decline in ESRD incidence (20,49). Additionally, we have explored the socio-economic consequences of T1D (52,53), developed risk equations for Type 2 Diabetes (54) and validated health-economic models (55). Ongoing work at the Swedish Institute for Health Economics (secondary affiliation of co-applicant [name]) includes the development of a health-economic model for T1D, initially focusing on adults (40) but with plans to incorporate childhood and adolescent risks for a full lifespan perspective. Preliminary data indicate that T1D in children has lasting effects on parental labour-market outcomes, suggesting a need to integrate a family impact module into health-economic models.

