#### **Hypothesis 1: The incidence of childhood-onset type 1 diabetes will peak in Sweden during the early 2020s.**

To deepen our knowledge on incidence trends and understand more of age-period and cohort effects in T1D incidence trends, we will make use of hierarchical Age-Period-Cohort (APC) analysis with covariates, see e.g. (60) for a comprehensive overview. Incident cases come from the PDR and covariates will come from the MBR concerning early pregnancy weight and gestational age and from the CHS regarding child growth (61). We will expand our previous analysis using non-linear semiparametric generalized additive models for count data (4,6). The time related changes we study are age effects (A), period effects (P) and shared life events for a set of individuals, i.e., cohort effects (C). The fitted APC models can be evaluated with model diagnostics and give (i) the magnitude of the individual APC effects. For example, the minimum and maximum values of the marginal APC effects and the overall size of each effect, (ii) an assessment of one-dimensional covariate smooth effects, for example for child weight or mother's weight respectively, and (iii) a table with full model results. Either a list of several models or for a single model, here both linear coefficients and all nonlinear estimates are returned. The work will resume during the latter part of the period, with IW and TL leading.

---

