In the analysis on the siblings, we use pharmacological information from the PDR, specifically data on antidepressants and compare them to non-related controls. We will retrieve health data from the NPR and the CDR and use LISA for socioeconomic variables. We will apply a non-parametric approach, focusing on population effects with analyses based on Persson et al (58). Both these studies will involve PhD-student [name].

---

**Hypothesis 4: Health-economic evaluation models require risk equations tailored for integration into Markov and microsimulation models. These equations must capture T1D-related complications and outcomes from childhood through middle age, reflecting current diabetes management practices.**

Modern T1D management has improved outcomes for individuals diagnosed in childhood, as well as their parents. We will use NPR data to develop a comprehensive set of risk equations predicting a wide range of T1D-related outcomes, including micro- and macrovascular complications such as myocardial infarction, stroke, heart failure, peripheral vascular disease, hypoglycaemia, hyperglycaemia, amputation, end-stage renal disease, and retinopathy. These analyses will incorporate time-to-event methods and assess excess risks for additional comorbidities, including psychiatric conditions and all-cause hospitalisations. Mortality risk estimates will also be included.

Risk factors such as age, diabetes duration, and clinical variables (e.g., HbA1c) will be considered. Sensitivity analyses will evaluate changes in risk estimates over time in response to evolving treatment recommendations. Additionally, the impact of T1D onset on parents will be examined using hospitalisation data (NPR) and employment-related records (LISA). We will compare T1D parents to control parents, adjusting for confounders such as sibling number, age, employment, and education using panel-data regression methods. This work, led by [name], will involve a PhD student based at Lund University with proximity to modelling expertise at the Swedish Institute for Health Economics (<https://ihe.se/>).

---

**Hypothesis 5: Target trial protocols can be specified for research questions lacking a pre-defined time zero, allowing for both cohort and case-control study designs in the SCDR. For research questions related to disease-free controls, a case-control sample analogue can be given.**

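### Does Hypothesis 4 undercut its own demand for up-to-date risk equations by leaving change over time to a sensitivity analysis?

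*Protocol*

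**What the plan says.** All passages are in the protocol.

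- **Project Description, Hypothesis 4, requirement.** The equations must cover "outcomes from childhood through middle age, reflecting current diabetes management practices".
- **Hypothesis 4, motivation.** "Modern T1D management has improved outcomes for individuals diagnosed in childhood, as well as their parents".
- **Hypothesis 4, data and model.** The National Patient Register is the source, with no years given, and the methods are time-to-event. On predictors: "Risk factors such as age, diabetes duration, and clinical variables (e.g., HbA1c) will be considered".
- **Hypothesis 4, change over time.** "Sensitivity analyses will evaluate changes in risk estimates over time in response to evolving treatment recommendations".
- **Survey of the Field, Health Economics.** Type 1 diabetes models have rested on an American trial, its follow-up study and frameworks borrowed from type 2 diabetes. The section asks for "the integration of risk equations derived from more recent patient cohorts, such as Swedish observational data". One use of such models is "assessing the value of delaying T1D onset in terms of patient outcomes and cost savings".
- **Preliminary and Previous Results, Health Economics.** The group's work "has demonstrated positive trends in T1D complications, including a decline in ESRD incidence".
- **Equipment.** The register holds cases from 1 July 1977 and was last updated in 2023.
- **Project Description, Hypothesis 1**, on incidence: "The time related changes we study are age effects (A), period effects (P) and shared life events", the last of these being the cohort effects.

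**The concern.** The protocol says that care has improved, that ESRD incidence has fallen and that the equations must describe current practice. It then names age, duration and clinical variables as predictors and mentions change over time only under sensitivity analyses. The register reaches back to 1977, so several treatment eras could be pooled. Hypothesis 1, by contrast, puts period and cohort effects into its main model.

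A simulation model runs on the base-case equation. If that equation averaged over earlier, worse decades, it would overstate today's complication rates. It would then also overstate the value of delaying onset, which is one of the uses the protocol names.

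**Working it through.** The protocol states no event rate, trend or data window for Hypothesis 4, so it has no figure to reproduce. There are two questions. Does the text commit to the harmful analysis? How large would the harm be if it did?

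**1. What the text commits to**

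| Needed for the concern to hold | What Hypothesis 4 says |
|---|---|
| All calendar years are pooled | Not said; no years are given |
| The base case omits calendar time | Not said; the predictors are examples and are to be considered |
| The base case need not be up to date | The reverse: up-to-date practice is a requirement on the equations |
| The sensitivity analysis replaces a current base case | Not said; it is an additional analysis |

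A base case fitted to recent follow-up, with a sensitivity analysis of how estimates moved over time, agrees with every sentence. So does a base case with a period term evaluated at the latest year. The sentences do not contradict each other.

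**2. The supporting passages**

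- The call for recent cohorts in the Survey of the Field contrasts older sources with newer ones and gives Swedish observational data as its example. Using this register answers that call. The sentence does not ask for a recent window within the register.
- Hypothesis 1 is about incidence trends, so period and cohort effects are what it sets out to estimate. Hypothesis 4 aims at prediction, and its main model need not have the same structure.

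**3. Size, if years were pooled with no period term (assumed inputs)**

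Person-time was enumerated by attained age, diagnosis date and calendar time on a 0.25-year grid. Diagnoses run from July 1977 to the end of 2023, with onset age uniform over 0-14. Numbers double from 1978 to 2008 and are then flat, in line with the Survey of the Field (more than doubled, then stable). The assumed hazard falls by calendar time t as exp(−r(t − 2023.5)), with r = 0.02 and none of the decline carried by HbA1c. The ratio is the pooled mean hazard divided by the 2023 hazard.

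| Data from | Ages 5-15 | Ages 45-55 |
|---|---|---|
| 1977 | 1.46 | 1.08 |
| 2005 | 1.20 | 1.08 |
| 2014 | 1.10 | 1.07 |

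At ages 15-25, r from 0.01 to 0.03 gives 1.17 to 1.64 for data from 1977, and 1.09 to 1.31 for data from 2005. If HbA1c carries the whole trend, the ratio is 1.00.

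A simpler two-era formula gives the same picture. Let w be the share of person-time from an earlier era and RR the current-to-earlier rate ratio. Then pooled/current = (w + (1 − w)·RR)/RR. With w = 0.5 and RR = 0.70 this is (0.5 + 0.35)/0.70 = 1.21. The protocol's only numerical trend is the fall in type 1 diabetes' share of ESRD cases from 10% to 5.6%, a ratio of 0.56. That is a share of cases and not an incidence rate, so it cannot supply RR.

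**4. Trend by year of diagnosis**

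If the 2% decline acts by year of diagnosis and the comparator is a child diagnosed in 2023, the ratio for data from 1977 is 1.73 at ages 15-25 and about 2.1 at ages 35-45. That child reaches 35-45 only decades from now, so this is a forecast error and not an error about current risk. Against people of the same age in 2023, the five ten-year age bands from 5-15 to 45-55 give 1.45, 1.34, 1.23, 1.12 and 1.03, close to the calendar-period result.

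**5. Direction**

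The Survey of the Field section on nephropathy leaves open whether present care lowers risk or only postpones progression, and Hypothesis 2 expects a later ESRD peak. Under postponement, a pooled equation could overpredict at short durations and underpredict at long ones. No trend is documented for psychiatric conditions or all-cause hospitalisation, which Hypothesis 4 also covers. Overprediction is therefore not assured.

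**The case for a change.** The strongest reply is that this is not mere silence. The protocol makes being current a requirement, and the one place where it deals with change over time is a sensitivity analysis. On that reading the essential property has been given a secondary role, and a later analysis plan would have to override that. The remedy would also be cheap: a stated target period, and a period term that discards no events.

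Part of this stands. A reader cannot tell from the protocol which years the base case will use, and one sentence would settle it. Pooling old follow-up without adjustment could also matter, most of all at young ages.

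The step from there to an error does not stand. Naming a sensitivity analysis of trends does not say that the base case ignores them, so an analysis plan that fixed a recent window would override nothing. The choice between a period term, a diagnosis-year term and a recent window is a modelling trade-off. A 2014-2023 window still leaves about 1.10 at ages 5-15 under the assumed 2% trend. It also keeps only 43% of the person-time available from 1977, which widens intervals about 1/√0.43 = 1.5 times. That choice belongs in the analysis plan.

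**Conclusion.** The concern does not hold. Hypothesis 4 requires equations that reflect present care, leaves the predictors open and adds an analysis of change over time. Nothing in it is wrong or contradictory. The missing detail, a calendar window and how time enters the model, is ordinary analysis-plan content, and that plan is not at hand.

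The harm depends on pooling early follow-up without adjustment, which the protocol does not propose and which its own requirement argues against. The ratios shown, from 1.00 to 1.64 against current risk in the calendar-period scenarios, rest on an assumed decline, an assumed data start and an assumed share carried by HbA1c. They show what would be at stake under a choice nobody has stated. They do not measure a fault in this plan.

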### International and National Collaboration

---

The research group itself is a nation-wide collaboration working on data from national registers.

Since 2015, IW is part of an international initiative for experts on observational data analysis, Strengthening Analytical Thinking for Observational Studies (STRATOS), (<http://www.stratos-initiative.org>). IW is co-chair of the STRATOS Topic Group 7: Causal Inference.

Since 2009, KSC is part of the Swedish Institute for Health Economics, an institute that during more than two decades has developed health-economic models for the evaluation of diabetes interventions (<https://ihe.se/>). The institute is a driving contributor to the Mount Hood Diabetes Challenge Network ([www.mthooldiabeteschallenge.com](http://www.mthooldiabeteschallenge.com)), an international collaboration with regular conferences focusing on comparing and exploring validations of health-economic simulation models in diabetes.

